## 10. Prior Approvals

- 10.1. There will not be any approvals obtained prior to commencing the research. The study was presented to [name] for approval, and the signed Departmental Review Form can be found in the “Supporting Documents” section.
- 10.2. This study does not include any ionizing radiation, biological specimens, or drugs.

## 11. Multi-Site Research

This is not a multi-site research study.

## 12. Procedures

This non-blinded, non-inferiority randomized controlled trial will be conducted at the UNM Eubank Clinic and SRMC Urogynecology clinic. Each site will recruit participants and we will plan to obtain up to 130 women between the two sites. Collaborating investigators will be members of the Urogynecology Division at UNM HSC.

The primary aim of our study is to determine if symptoms and quality of life related to overactive bladder are improved similarly with TENS use versus PTNS in women with OAB/UUI. The target population will be patients with OAB or UUI who are seeking care after failing first- and second-line therapies. According to the American Urologic Association, first line therapy includes conservative treatments like bladder training, bladder-control strategies, pelvic floor muscle training or fluid management. Second-line treatment includes pharmacologic management with anti-muscarinic and  $\beta$ 3-adrenoceptor agonist medications. Subjects must have failed a trial of at least one medication (use with no improvement in symptoms for at least 8 weeks, or a contraindication to taking medication such as narrow angle glaucoma, use of other medications that would interact with anticholinergics, uncontrolled hypertension, allergic reaction or adverse side effect to an anticholinergic medication). The subject may have stress urinary incontinence, but urinary urgency or urgency urinary incontinence must be a bothersome complaint or symptom. The current standard-of-care recommendation for those with refractory OAB or UUI who have failed first- and second-line therapies is to offer patients third-line treatment with PTNS, sacral neuromodulation, or intradetrusor injection of onabotulinumtoxinA. For patients who present for treatment of refractory OAB or UUI, we will take a thorough history and physical and counsel the patient on all of her options including medical and surgical interventions.

If the patient is interested in non-surgical management with PTNS and fulfills study inclusion criteria, we will then offer her the choice of volunteering for the study. All women will give written and/or electronic consent prior to their enrollment at this time and fill out baseline questionnaires in the clinic. Research staff and clinicians will obtain consent and administer study. After enrollment, participants will fill out a baseline OAB-q and will be

PROTOCOL TITLE: INTENSE: INvestigation of TENS Efficacy versus Posterior Tibial Nerve Stimulation for overactive bladder

given a 3-day voiding diary to complete prior to starting their intervention. Urinalysis and urine culture will be obtained to rule out urinary tract infection. This is routinely done on all new patients in our clinic and would be performed on patients not participating in the study as well. Data collected in addition to the above outcome measures includes patient demographics, medical/surgical history, and contact information, which are attached as supporting documents. This information will be collected from the patient on the day of enrollment and we will review the patient's medical record if information is missing or unclear.

The randomization sequence will be generated by computer-based randomization in a sequence that preserves 1:1 randomization and also preserves allocation concealment (likely with randomly alternating block sizes of 6-10 in blocked randomization). Randomization assignments will be completed via REDCAP by a research coordinator. Randomization will only occur after consent has been signed and all baseline data has been obtained.

*12.1. Interventions:*

*12.1.1. PTNS:* Women randomized to the PTNS group will begin therapy after their baseline evaluation is complete. They will be scheduled for PTNS treatment sessions once weekly for 30 minutes, for 12 weeks total. PTNS treatment will be performed as follows:

- The patient sits in a reclining chair, with their legs elevated on a foot rest. The area for needle placement is cleaned with an alcohol swab. A 34 gauge needle is inserted percutaneously approximately 5 cm cephalad to the medial malleolus of the right or left ankle (patient's choice) at a 60 degree angle. A surface electrode is placed on the medial aspect of the ipsilateral calcaneus. The needle and electrode are connected to a low voltage (9V) electrical stimulator (brand name). Stimulation current with a fixed frequency of 20 Hz and a pulse width of 200  $\mu$ sec is increased until flexion of the big toe or fanning of all toes visualized, or until the woman reports a tingling sensation across the heel or sole of the foot. The current is then set to the highest level of tolerable to the patient (0-10 mA) and then she undergoes therapy for 30 minutes. If no response is seen (no fanning of toes or flexion of big toe or no report of a tingling sensation across the heel or bottom of the foot), the needle is replaced on the same or opposite side until the appropriate response is seen. The needle placement sites will be monitored for bleeding, bruising, irritation or a hematoma. This will be repeated each week, until the completion of 12 weeks of treatment.
- If women assigned to the PTNS arm miss one of their weekly office PTNS sessions, they will be permitted to "make up" the missed session at the end of the 12 weeks, and their "12 week" outcome measures will be performed following that last session (13 weeks following randomization). Women that have missed this one session and made up the session at the end of the treatment course will be considered "fully compliant" with treatment and analyzed in the "per protocol" analysis as having completed the PTNS treatment course per protocol.
- If women assigned to the PTNS arm miss more than one of their weekly office PTNS sessions, they will not be allowed to make up the extra sessions and their

PROTOCOL TITLE: INTENSE: INvestigation of TENS Efficacy versus Posterior Tibial Nerve Stimulation for overactive bladder

participation in the study or outcome measurement will not be extended further than 13 weeks after randomization. However, they will not be withdrawn from the study for missing sessions, and will be followed for outcomes and adverse events despite missing sessions of PTNS. Women that miss more than one session of PTNS or miss one session and do not make it up at the end will be considered “not fully compliant” with PTNS treatment, and will be analyzed in the “intention-to-treat” analysis in the PTNS arm but not in the “per protocol” analysis in the PTNS arm.

Prior to their week 6 session, women will be asked to complete a 3-day voiding diary in the three days before their scheduled PTNS treatment and bring it to clinic. At their week 6 session, women will complete the UDI and PSQ questionnaires via REDCAP on an iPad in clinic. The same will be conducted for their week 12 session. Patient compliance of attending PTNS sessions will be recorded.

**12.1.2. TENS:** Women randomized to the TENS groups will begin therapy after their baseline evaluation is complete. They will be asked to purchase a TENS 7000 device (estimated cost \$30) and will administer self-treatment at home, daily for 20 minutes, for 12 weeks total. Current practice in the Urogynecology clinic is to offer TENS therapy to women as an alternative to in-person maintenance therapy for after completing PTNS 12 sessions. TENS 7000 device is off label for its use in the treatment of OAB. If funding is secured, women in both PTNS and TENS group will be reimbursed with a merchandise card. Participants will be asked to bring their device to clinic to ensure the correct device is used, standardize settings and provide the following patient education:

- Proper TENS device set up and pre-set standardized settings, detailed below
- Proper electrode pad placement that will be demonstrated. Electrodes will be traced with a skin marker during this clinic visit and pictures will be provided to ensure correct placement at home. If the patient has a camera, they can photograph electrode placement while in clinic.
- Determine intensity level
- Patients will be notified that they can go about their regular daily activities with the TENS device in place, so that treatment does not interfere with normal work or household duties. However, they will be instructed to not use the device while exercising due to sweat causing reduced adhesive function of electrodes and possible displacement.
- If a caretaker will be assisting the participant in use of the TENS unit due to physical limitations, they too will be instructed in set-up and use.
- An information handout with device settings, surface electrode placement, and treatment schedule will be provided at this initial clinic visit.

TENS treatment will be performed as follows (adapted from the most common setting from a systematic review of TENS for OAB):

- Surface electrodes, 2 x 2 in diameter, will be placed 5 cm cephalad to the medial malleolus of the right or left ankle (patient’s choice). The second surface electrode is placed on the medial aspect of the ipsilateral calcaneus. The electrodes are connected to the TENS device with the following pre-set settings:
- Mode: “M” or modulation

PROTOCOL TITLE: INTENSE: INvestigation of TENS Efficacy versus Posterior Tibial Nerve Stimulation for overactive bladder

- Frequency: 10 Hz
- Pulse width: 200  $\mu$ sec
- Intensity: to patient comfort level, as determined at clinic visit when device is verified. This is variable and participants will be told that as they use the device regularly, it is anticipated that they will become accustomed to stimulation and may need to change this setting.
- Women will then complete 20-minute daily TENS treatment using the settings above, for 12 weeks total.
- If women assigned to the TENS arm miss more than 2 daily sessions in a week on one of their weeks of treatment, they will be permitted to “make up” the missed sessions with an extra week of treatment at the end of the 12 weeks, and their “12 week” outcome measures will be performed following that week of make-up (13 weeks following randomization). Women that had this one “deficient week” with less than 5 treatments in a week and made up a week (with 5 or more daily treatments in the last week), their treatment course will be considered “fully compliant” with treatment and analyzed in the “per protocol” analysis as having completed the TENS treatment course per protocol.

- 12.2.3 **PSQ:** The Patient Satisfaction Question is a validated tool to assess patient satisfaction of treatment. It is comprised of a single question and is widely used in OAB/UUI.

### 13.Data Analysis

- 13.1. *Data Analysis:* Between and within group differences will be evaluated using Fisher's exact test for categorical variables and t-tests for continuous variables, as we expect the data will be normally distributed. Wilcoxon rank-sum test will be used for continuous variables that are not normally distributed. If there are any baseline differences between groups, a multivariate analysis will determine the contribution of these differences to observed differences (if any) between groups.
- 13.2. *Intention-to-treat analysis:* We plan to perform the primary analysis as "intention-to-treat" indicating that patients will be analyzed in the group to which they were randomized, regardless of compliance with study procedures, unless they asked to be withdrawn or were withdrawn by investigators due to safety or validity concerns. For example, PTNS patients that miss more than one session or do not make up a missed session of their office PTNS would still be analyzed in the "intention-to-treat" analysis as being in the PTNS group.
- 13.3. *Per protocol analysis:* We plan to perform a secondary analysis as "per protocol" indicating that patients will be analyzed in the group to which they were randomized only if they complete a full 12 weeks of treatment in compliance with study procedures, meaning that women assigned to the PTNS arm completed 12 weekly PTNS sessions in the office in 13 weeks or less, and women in the at-home TENS arm performed TENS stimulation at least 5 days per week for 12 weeks, as averaged over 12 weeks. For example, PTNS patients that miss more than one session or do not make up a missed session of their office PTNS will not be analyzed in the "per protocol" analysis as being in the PTNS group.
- 13.4. *Power Analysis:* Power analysis was performed based on previously reported means and standard deviation for the OAB-q. The primary outcome of this study is improvement in HRQL and symptom bother of OAB/UUI as measured by the OAB-q. We used the means and standard deviation for this questionnaire from a prior unpublished pilot RCT from Walter Reed comparing PTNS and TENS for the treatment of OAB. We have assumed a change score of greater than 10 points to be significant between groups based on the minimally important difference that has been previously established. To achieve significance for a non-inferiority study using these assumptions we would need 80 patients,

40 per group to detect this difference with  $\alpha = 0.05$  and 80% power. To allow for a dropout of up to 30% we will enroll up to 130 patients to account for participants who are lost to follow up. As noted above, we plan to perform both per-protocol and intention-to-treat analysis, and adequate power must be achieved for both per-protocol and intention-to-treat analysis, with the per-protocol patients (those in the PTNS group completing at 12 treatments in a total of 13 weeks) being expected to be a lower sample size and take more recruitment and study follow-up to achieve power.

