## 1. Objectives

- 1.1. The objective of this research is to perform a non-masked, non-inferiority randomized controlled trial to assess the quality of life (QOL) of women with idiopathic overactive bladder (OAB) before and after treatment with percutaneous tibial nerve stimulation (PTNS) or transcutaneous electrical nerve stimulation (TENS) of tibial nerve. The target population is patients with OAB who previously failed first- and second-line treatments and desire non-surgical management.
- 1.2. Our central hypothesis is that a TENS unit is non-inferior to PTNS for improving the quality of life and symptom distress of women with OAB. The specific aims are:
  - 1.2.1. To compare the effects on health-related quality of life (HRQoL) and symptom bother as measured by the change in score from baseline of the Overactive Bladder questionnaire (OAB-q) in women with urgency urinary incontinence or overactive bladder before and after PTNS versus TENS after 3 months of therapy. Secondary outcomes related to this aim include change in symptom bother alone, as measured by the OAB-q symptom subscale and change in HRQL alone, as measured by the OAB-q HRQL subscale from baseline. **Hypothesis:** TENS will demonstrate similar effects on symptoms and symptom-associated HRQoL in the treatment of women with OAB compared to PTNS.
  - 1.2.2. To compare the rates of treatment success, as defined as 50% or more reduction of urinary incontinence episodes or 25% or more reduction in day or night voids in women with OAB before and after PTNS versus TENS after 3 months of therapy. The number of urinary incontinence episodes, number of voids per day and number of voids per night will be measured by a three-day voiding diary. **Hypothesis:** TENS will demonstrate similar rates of treatment success in women with OAB compared to PTNS.
  - 1.2.3. To perform a comparative analysis of patient satisfaction and compliance between TENS and PTNS. Patient satisfaction will be measured by a patient satisfaction question (PSQ). Patient compliance will be measured by number of treatment sessions completed as verified by clinical records of completed PTNS treatments and TENS device interrogation. **Hypothesis:** Women will be satisfied with both TENS and PTNS treatment and will have greater treatment compliance with TENS compared to PTNS.

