## 5. Number of Subjects

5.1. This is a single-center study at the University of New Mexico, therefore the total number of subjects at the University of New Mexico is the total number of subjects for the study.

5.2. The total number of subjects to be recruited at this site is up to 130 patients.

5.3. *Sample size calculation:* The primary outcome for this study is the change in the OAB-q total score from baseline to 3 months. We used the means and standard deviation for this questionnaire from an unpublished pilot RCT study from Walter Reed that compares PTNS and TENS for the treatment of OAB (unpublished work). We have powered the study based on a 10-point difference as significant between groups. This 10-point difference used for the power calculation is based on the previously established minimum important difference. To achieve power for this non-inferiority RCT study showing that the difference between groups is less than 10 points, we need 40 patients per group (80 total) to detect no difference with  $\alpha = 0.05$  and 80% power. Allowing for dropout of up to 30%, we will aim to randomize 114 patients, and will plan to recruit up to 130 to allow for potentially higher drop-out, as the study primary outcome is at the 12 weeks' time point. As we plan to perform both per-protocol and intention-to-treat analysis, the sample size must be met for both per-protocol and intention-to-treat analysis, with the per-protocol patients (those in the PTNS group completing at 12 treatments in a total of 13 weeks) being expected to be a lower sample size.

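### Section 13.1 gives within-arm (before-after) comparisons the same tests as between-arm ones, so non-normal outcomes would get a rank-sum test on paired data

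*Combined protocol and SAP*

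**What the plan says.** Section 13.1 (Data Analysis) covers both kinds of comparison in one sentence, which opens "Between and within group differences will be evaluated using" and goes on to assign Fisher's exact to categorical data and t-tests to continuous data. It expects normal data and adds a fallback: "Wilcoxon rank-sum test will be used for continuous variables that are not normally distributed". It does not set out separate methods for within-arm comparisons, and the documents nowhere mention a paired t-test, a signed-rank test, McNemar's test or a repeated-measures model.

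The within-arm data are repeated measures. Table 1 in section 12 schedules the OAB-q and the three-day voiding diary for the same women at baseline, 6 weeks and 12 weeks. Section 1.1 describes assessing quality of life "before and after treatment with percutaneous tibial nerve stimulation (PTNS) or transcutaneous electrical nerve stimulation (TENS) of tibial nerve". The primary outcome is itself a change score: "The primary outcome for this study is the change in the OAB-q total score from baseline to 3 months" (section 5.3).

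**The concern.** The rank-sum and Fisher's exact tests treat the two sets of values as coming from different people. Used on baseline and 12-week values from one arm, they set the change against the spread between women. A paired test sets it against the spread of each woman's own change. If a woman's two values are positively correlated, the independent-samples p-value is too large.

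What is at stake is the before-after statement for each arm. The trial has no sham or untreated arm, so readers will look at within-arm change to see whether women improved at all. A real improvement in, say, incontinence episodes could be reported as non-significant because of the test chosen.

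**Working it through.** **Inputs.** From the documents: 40 women per group ("we need 40 patients per group (80 total) to detect no difference with", section 5.3), alpha 0.05 and 80% power. Not in the documents: the before-after correlation rho, the outcome SD and the expected within-arm improvement. Rho is therefore assumed at 0, 0.3, 0.5 and 0.7, and the improvement at 0.4 to 0.8 SD. Tests are two-sided at 0.05.

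**The plan's own figure.** The 40 per group cannot be reproduced, because the SD is cited only to an unpublished pilot ("We used the means and standard deviation for this questionnaire from an unpublished pilot RCT study from Walter Reed"). With a 10-point margin and no true difference, n = 2 SD² (z₁₋α + z₀.₈)² / 10². Setting n = 40 gives SD = 10 × √20 / (z₁₋α + z₀.₈).
- One-sided alpha 0.05: 44.72 / (1.645 + 0.842) = about 18.0.
- One-sided alpha 0.025: 44.72 / (1.960 + 0.842) = about 16.0.

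The dropout step agrees with the plan: 80 / 0.7 = 114.3, stated as 114. Nothing below depends on these figures, because the sample size concerns the between-arm comparison.

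**False-positive rate on paired data.** For equal variances, the true standard error of a mean change is √(1 − rho) times the one an unpaired test uses. An unpaired test at nominal 5% therefore rejects with probability 2 × [1 − Φ(1.96 / √(1 − rho))]. That is 1.9% at rho 0.3, 0.6% at 0.5 and 0.03% at 0.7. This formula is for an unpaired comparison of means; the rank-sum test was simulated directly, with 40 pairs of bivariate normal values and no true change:

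| rho | Rank-sum | Signed-rank |
|---|---|---|
| 0 | 4.9% | 4.8% |
| 0.3 | 2.1% | 4.9% |
| 0.5 | 0.6% | 4.5% |
| 0.7 | 0.1% | 4.9% |

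A separate run gave 0.5% for rank-sum at rho 0.5, the same within simulation error.

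**Power, rho 0.5, 40 women.**

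| Assumed improvement | Rank-sum | Signed-rank |
|---|---|---|
| 0.4 SD | 36-38% | 67% |
| 0.5 SD | 61% | 85% |
| 0.6 SD | 80% | 96% |
| 0.8 SD | 98% | 99.9% |

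At 0.4 SD the gap also depends on rho: about 39% versus 53% at rho 0.3, and 34% versus 87% at rho 0.7. At rho 0 there is no loss (58% versus 56% at 0.5 SD).

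**Binary items, 40 women, rho 0.5.** With 50% at both times, Fisher's exact rejects 0.3% of the time and exact McNemar 2.3%. For a change from 50% to 75%, power is 58% and 88%. These figures matter only if a paired binary item is analysed. The PSQ has no baseline value in Table 1, and treatment success in section 1.2.2 is already defined by change, so there are few such items.

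**Limit of the check.** The simulated continuous data are normal, which isolates the effect of ignoring the pairing. Skewed diary counts with ties would give different figures.

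**The case against.** The strongest reply is that little of the trial rests on within-arm tests. Although section 1.1 speaks of before and after, specific aims 1.2.1 to 1.2.3 all compare PTNS with TENS. Section 7.1 sets the primary endpoint as a comparison of change between arms, and no within-arm test is listed as an endpoint. That stands, and it makes this a correction to supportive analyses.

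Second, the plan expects normal data, so t-tests are the main route and rank-sum the fallback. The word t-tests includes the paired form. A reader might infer that every within-arm standard error will be too large by 1/√(1 − rho), or 1.41 times at rho 0.5. The documents do not support that: the ratio applies only if the t-tests are run unpaired, which the plan neither says nor rules out.

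Third, the power loss depends on an improvement that the documents do not give. At 0.8 SD it is about two percentage points. With 57 per arm (114 / 2, no dropout), 0.6 SD and rho 0.5, power is 95% versus 99%. This stands too, and no single gap should be quoted alone.

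What the reply does not remove is that the stated rule sends non-normal within-arm comparisons to the rank-sum test. An analyst might use a paired test anyway, but would then depart from the plan, possibly after seeing the data. Taking change scores does not help within one arm, because rank-sum still needs two independent samples.

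**Conclusion.** The point holds for within-arm comparisons. As written, section 13.1 prescribes independent-samples tests for paired data when a continuous outcome is non-normal, and Fisher's exact for any paired binary item. Diary counts are the likeliest place for it to matter; that they will be non-normal is a judgement, not something the documents state.

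The size depends on the assumed rho and improvement: from no loss at rho 0, to roughly 30 percentage points of power at rho 0.5 and 0.4 SD, and back to almost none at 0.8 SD.

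Two stronger readings are not supported. A reader might infer that the trial could falsely claim improvement; with positive correlation the error runs the other way, making such claims rarer than 5%. A reader might also infer that the non-inferiority result or the 40 per group is compromised. The arms are independent groups of women, so comparing change scores between them does not break the independence that these tests require, and the sample size does not use the within-arm tests.

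**What to change.** In section 13.1, limit Fisher's exact and the rank-sum test to between-arm comparisons. For within-arm change, name the paired t-test, or the Wilcoxon signed-rank test if the changes are not normal, and McNemar's test for any paired binary item. Label these analyses as supportive. Reporting within-arm change descriptively, with confidence intervals based on each woman's own change, would also be acceptable. The cost is one sentence in the plan; no extra data or participants are needed.

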## 7. Study Endpoints:

- 7.1. The **primary endpoint** of our study is to determine the change in OAB-q score in patients who undergo 12 weeks of PTNS compared to those who undergo TENS therapy for OAB. Our secondary endpoints include change in OAB-q Symptom Bother subscale score from baseline, change in OAB-q HRQL subscale score from baseline, number or urinary incontinence episodes, number of voids per day, number of voids per night, patient satisfaction question (PSQ) and patient compliance.
- 7.2. Due to the extremely low risk of the therapeutic interventions, we do not have any **safety endpoints**.
- 7.3. Our **exploratory endpoints** are to investigate compliance with treatment between groups and preference between therapeutic options.

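### Section 13.1 names no test that uses the order of answers, which would cost power on the satisfaction question (PSQ) if its answers are graded

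*Combined protocol and SAP*

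**What the plan says.** Section 13.1 covers all outcomes in general terms: "Between and within group differences will be evaluated using" Fisher's "exact test for categorical variables and t-tests for continuous variables". It adds that the "Wilcoxon rank-sum test will be used for continuous variables that are not normally distributed". The rest of section 13 deals with analysis sets and with power for the OAB-q. None of it mentions ordered categories or names the PSQ.

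Section 7.1 lists the "patient satisfaction question (PSQ) and patient compliance" among the secondary endpoints. Aim 1.2.3 undertakes "To perform a comparative analysis of patient satisfaction and compliance between TENS and PTNS", with the PSQ as the measure of satisfaction, and its hypothesis on satisfaction is that "Women will be satisfied with both TENS and PTNS treatment". Section 12.2.3 is the only description of the instrument: "It is comprised of a single question and is widely used in OAB/UUI". It does not give the number, wording or order of the answers. Table 1 collects the PSQ at 6 and 12 weeks.

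**The concern.** Satisfaction questions are often graded. If this one is, 13.1 offers it two classes, and a single graded item most naturally counts as categorical, which leads to Fisher's exact test. For more than two answers that test treats the answers as unordered labels: a shift from the middle to the top counts no differently from any other rearrangement of the same rarity.

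At stake is the efficiency of one secondary comparison. A real difference in satisfaction between home TENS and office PTNS would be missed more often than it need be. A non-significant p-value from the weaker test, with no estimate beside it, would also say little about whether the two arms are similarly satisfied.

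**Working it through.** **The plan's own figures.** No power, effect size or margin is stated for the PSQ, so there is no figure to reproduce. The numbers per arm come from section 5.3: 40 per group for the primary endpoint, and 114 randomized, or 114/2 = 57 per arm. The dropout step agrees: 80/(1 − 0.30) = 114.3. The 40 itself cannot be checked because no SD is given; it serves here only as a plausible evaluable number. 57 per arm means no losses.

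**Why Fisher ignores order.** With answer totals c_j over both arms, counts a_j in one arm, n women in that arm and N in all, the exact test ranks tables by

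P = Π_j C(c_j, a_j) / C(N, n).

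The product is the same whichever answer is called first, second or third, so the p-value is too. The rank-sum test uses midranks, which follow the order, with tie-corrected variance

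V = (n1·n2/12)·[(N + 1) − Σ(c_j³ − c_j)/(N(N − 1))].

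**Assumed inputs, none of them from the documents.** Two to five levels, the answer distributions shown, a proportional-odds shift with odds ratio (OR) 2 to 3, and two-sided 0.05. For example, take answers 50/35/15% in one arm and OR 2.5:

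- cumulative proportions 0.50 and 0.85 give odds 1.00 and 5.67;
- divided by 2.5, these become 0.40 and 2.27;
- back-transformed, 0.286 and 0.694, so the other arm has about 29/41/31%.

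**Simulated power, exact r × c Fisher → tie-corrected rank-sum, in percent** (gap in points, taken before rounding):

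| Levels | OR | 40 per arm | 57 per arm |
|---|---|---|---|
| 3 (50/35/15) | 2 | 27.5 → 36.1 (8.6) | 41.8 → 52.2 (10.4) |
| 3 (50/35/15) | 2.5 | 46.4 → 59.0 (12.6) | 64.1 → 74.7 (10.6) |
| 3 (50/35/15) | 3 | 63.5 → 74.7 (11.3) | 80.1 → 88.3 (8.2) |
| 4 (equal) | 2 | 24.8 → 38.4 (13.6) | 35.0 → 52.5 (17.5) |
| 4 (equal) | 2.5 | 43.9 → 60.0 (16.1) | 59.9 → 76.8 (16.9) |
| 4 (equal) | 3 | 57.9 → 75.3 (17.4) | 76.5 → 89.0 (12.5) |
| 5 (equal) | 2 | 28.0 → 43.8 (15.8) | 30.4 → 50.8 (20.4) |
| 5 (equal) | 3 | 56.0 → 78.0 (22.0) | 76.8 → 89.6 (12.8) |

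Other distributions agree. Three levels at 60/30/10, OR 3 and 57 per arm give the smallest gap, 7.5. Four levels at 10/20/30/40, OR 3 and 40 per arm give 59.4 → 77.3 (17.9). Five levels at 10/15/20/25/30, OR 2.5 and 40 per arm give 41.6 → 63.4 (21.8). At OR 3.5 the gain falls to about 5 to 9 points with three levels and 9 to 15 with four.

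**Precision.** The Monte Carlo standard error of one power figure is at most √(0.25/3000) = 0.9 points for the three-level rows, √(0.25/1500) = 1.3 for four levels and √(0.25/500) = 2.2 for five. The ranges quoted are rounded outward for three and four levels, and the five-level top end is uncertain by several points.

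**Validity.** At OR 1, with three or four levels, Fisher rejects in 4.2 to 5.1% of trials and the rank-sum test in 4.4 to 5.9%. The gain is therefore not bought with a materially higher false-positive rate.

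**Two levels.** A gap of 5.1 to 9.5 points remains at OR 2 to 3, but there is no order to lose. It reflects Fisher's conservatism: 2.8 to 3.1% rejections at OR 1, against 4.5 to 5.6% for the large-sample test.

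**The case against.** The strongest reply is that the documents never call the PSQ graded and never assign it to Fisher's exact test. If it is scored as a number, 13.1 could send it to the t-test, or to the rank-sum test where it is not normal, which is the remedy proposed here. If it is yes/no, there is nothing to repair. This stands: the point is conditional on the response scale. But no reading of 13.1 tells the analyst which class the item belongs to, and in an unmasked trial that is better settled beforehand.

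A reader might infer more than the documents support:

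- That every categorical outcome loses power. Treatment success (aim 1.2.2) is defined by thresholds, "50% or more reduction of urinary incontinence episodes or 25% or more reduction in day or night voids", so it is binary and has no order.
- That the loss in power is a property of this plan. It depends on assumed levels, distributions, odds ratios and proportional odds.
- That the planned test is wrong. It keeps its error rate; only efficiency is affected.

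It can also be said that no between-arm difference in satisfaction is hypothesised, so low power there contradicts nothing. It is true that no stated figure changes. But aim 1.2.3 still promises a comparison between arms, and if the expectation is that women like both treatments, an estimate with an interval supports it better than a non-significant p-value.

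Finally, a proportional-odds model adds an assumption and can be unstable with sparse categories at about 40 per arm. That is fair, and it is why the rank-sum test should be the main test and the model only one way to obtain an estimate.

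**Conclusion.** The point holds in conditional form. Section 13.1 has no method for ordered categories, and the PSQ is the one named endpoint that may need one. If it has three or more ordered levels and is analysed as categorical, then under proportional odds with odds ratios of 2 to 3 and 40 to 57 per arm, Fisher's exact test gives up roughly 7 to 13 points of power with three levels, 11 to 18 with four and up to about 22 with five. With two levels no order is lost. The OAB-q analysis, the sample size, treatment success and all stated power figures are untouched. This is a free improvement, not a defect that threatens the trial.

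**What to change.** Add to section 13.1:

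- the PSQ response options, and whether they are ordered;
- if they are ordered, that arms are compared at weeks 6 and 12 by the tie-corrected Wilcoxon rank-sum test, reported with an effect estimate and 95% confidence interval, for example a common odds ratio from a proportional-odds model where the categories are not too sparse;
- that Fisher's exact test is kept for two-level or unordered variables.

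If the PSQ turns out to be yes/no, saying so closes the gap. The cost is one or two sentences written before the data are analysed. No new data, visits or participants are needed.
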